Beliefs about Vaccine-Preventable Diseases and Vaccination (Objective 2):

Belief measures will include participants' beliefs about the target diseases and vaccination and trust in healthcare providers and peers as information sources. Multiple studies evaluating vaccinations in older and minority populations have found that people who do not receive certain vaccinations are unaware of their risk of disease, do not believe they are susceptible to the disease, and are not aware of their eligibility to receive the vaccine or feel that the vaccine would not reliably prevent illness. ^{28,36-38} In contrast, literature indicates that those who reported receiving a vaccination understood their susceptibility to infection, were aware of their eligibility to receive a vaccination, received a recommendation from a healthcare provider and felt that vaccination was the best way to prevent disease. ^{28,40}

Our prior PPPP study demonstrated that a pharmacist-delivered educational program can increase participants' trust in pharmacists both as vaccinators and sources of information, but that such gains are short term (limited to the post-test). This finding suggests that pharmacist-delivered information does not lead to sustained trust in pharmacists. However, peers may be more readily accepted as an information source in this population, which may contribute to sustained trust. Thus the change in beliefs from baseline to post test and one month after the intervention will be assessed in both the PHARM and PEER groups to determine whether the PEER group experiences a greater level of sustained trust vs. the PHARM group.

Cost Analysis (Objective 3):

We propose to conduct a detailed cost analysis which examines PHARM and PEER intervention costs in terms of what each of these two programs cost per program participant. This will enable us to understand which approach, PHARM or PEER, is less costly to deliver. We hypothesize that PEER will be less costly then PHARM due to differences in staffing requirements. In fact, the main reason for inclusion of cost in the proposed study is to determine whether PHARM and PEER, each of which is less resource intensive then our prior pneumonia program, will be less costly but yield comparable efficacy.

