2.7.3 Sample Size Justification

The sample size was calculated using G*Power 3.0.10 and is based on the primary outcome measure (difference between change in mean knowledge score from baseline to 1 month for PHARM vs PEER). We plan to use a two-tailed independent samples t-test with α =0.05 to determine the between-group difference in mean knowledge scores at each timepoint. We seek to examine the difference, if any, in the effectiveness of the two approaches, PHARM and PEER; specifically, we wish to determine if the two approaches have similar results to within 20% difference expecting large variability (50% standard deviation). This difference is detectable at a power of 0.8 with 121 participants in each arm of the study. To ensure an adequate sample size, we scaled up the sample size calculation using the attrition rate from the prior pneumonia project. Attrition rate in PPPP was $\frac{203-143}{203}$ =0.296 ≈30%; thus scaling up by 30% yields a total sample size of 316 (158 in each arm).

As a secondary outcome, consistent with the prior pneumonia project, we plan to use a two-tailed paired samples t-test to determine the within-group difference in mean knowledge score between timepoints. However, because within-group differences are easier to detect than between-group differences, the sample size is powered to detect the 20% between-group difference.

2.8 Specific Drug Supply Requirements	None – vaccination is not included as a component of this study.	
2.9 Adverse Experience Reporting	Not required since vaccination is not being offered through this study.	
2.10 Itemized Study Budget	Provided as attachment.	

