TITLE: Randomized Trial of Peer-to-Peer Versus Pharmacist Education to

Improve Older Adults' Vaccination Knowledge Through the Senior Center Model of Care

CLINICALTRIALS.GOV

NCT NUMBER

NCT03239665

March 6, 2020 **DOCUMENT DATE:**

Overview of Statistical Analysis

The design of the study was a randomized trial with randomization to PHARM or PEER performed at the program date level. The primary outcome measure was a between-group comparison of change in knowledge for PHARM vs. PEER at BL vs. PT, and BL vs. M1. Secondary measures included between-group examinations of beliefs, trust, and activation at all 3 time points (BL vs. PT and M1). We also measured within-group differences in knowledge, beliefs, and activation and the intervention costs of PHARM and PEER, including program development, training and implementation.

Study data was recorded using paper forms and input into SAS Version 9.4 for analysis. Electronic data was password-protected by CIP while enrollment and data collection were ongoing. Files were checked to ensure de-identification prior to sharing with the Rutgers University investigators who completed the analyses.

Analysis was performed using an Intention-to-Treat (ITT) sample. This sample included all participants meeting study including criteria with ≥ 1 documented response from the baseline survey. In the case of missing data from the post-intervention or one-month follow-up survey, the matrix below was used to carry forward observations. For all tests, the significance level was chosen as $\alpha = 0.05$, and was downward adjusted via the Bonferroni method when appropriate.

Table 1. ITT approach for handling missing follow-up data.

BL Data	PT Data	M1 Data
Present	Present	Absent Utilize PT Data
Present	Absent	Present
	Utilize BL Data	
Present	Absent	Absent
	Utilize BL Data	Utilize BL Data

^{*}BL = baseline, PT = post-intervention, M1 = one-month follow-up

Baseline Demographics

Demographic analysis was carried out via t-test for continuous variables and Chi-square test for categorical variables.

Knowledge

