The number of correct responses to the knowledge items at each timepoint was calculated as a whole and by disease (pneumonia, influenza, zoster). Baseline knowledge was compared by race via Kruskal-Wallis test. Because the knowledge data were expected to be non-normal and integer-valued, knowledge items were assessed using nonparametric methods. Specifically, between-group differences in knowledge were assessed at each timepoint via Wilcoxon Rank-Sum test. Similarly, between-group knowledge differences across timepoints were assessed pairwise via Wilcoxon Rank-Sum tests with Bonferroni-corrected significance threshold of

 α =0.05/3=0.0167. Within-group differences in knowledge score across timepoints were tested pairwise using Wilcoxon Signed-Rank tests.

Beliefs

The percentage of respondents answering "Completely Agree" to each item at each timepoint was calculated and compared between PHARM and PEER, as in our PPPP study. Pairwise Wilcoxon Signed-Rank tests were run comparing within-group changes in beliefs across timepoints applying Bonferroni correction (α =0.05/3=0.0167). Either Chi-Square or Fisher's Exact tests were used to compare beliefs between groups at each timepoint, depending on expected cell counts.

Activation

For all participants, Chi-Square or Fisher's Exact testing was performed as appropriate at each timepoint to assess between-group differences in proportions of participants planning actions, including planning vaccination and planning to speak with a doctor, pharmacist, or family/friends, as well as actions taken, including vaccinations obtained and having spoken with a doctor, pharmacist, or family/friends.

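### Within-arm belief tests: Holm's step-down would give the same 5% family-wise control as the fixed 0.0167 threshold with somewhat more power (an optional efficiency gain, not an error)

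*SAP*

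**What the plan says.** The Beliefs section of the SAP sets the within-arm tests: "Pairwise Wilcoxon Signed-Rank tests were run comparing within-group changes in beliefs across timepoints applying Bonferroni correction", with the threshold given as 0.05/3 = 0.0167. With three timepoints there are three pairs per item and arm, and each has the same cut-off. No stepwise procedure is mentioned.

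The SAP overview gives a general rule. Alpha is 0.05 and "was downward adjusted via the Bonferroni method when appropriate".

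The within-arm knowledge tests have the same three-pair structure but no threshold of their own: "Within-group differences in knowledge score across timepoints were tested pairwise using Wilcoxon Signed-Rank tests". Section 2.7.3 of the protocol lists the within-arm knowledge comparison as a secondary outcome, there with a paired t-test: "we plan to use a two-tailed paired samples t-test to determine the within-group difference in mean knowledge score between timepoints".

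Hypothesis 2 (protocol section 2.1.1) is that both programs improve beliefs, which is a within-arm claim. Section 2.7.2 adds that "the change in beliefs from baseline to post test and one month after the intervention will be assessed" in both groups, but the purpose it gives is to see whether trust is better sustained with PEER than with PHARM. That is a between-arm question.

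**The concern.** Single-step Bonferroni holds all three pairs at 0.0167 whatever the other two show. Holm starts at the same 0.0167 for the smallest p-value, then relaxes to 0.025 and 0.05 as hypotheses are rejected. It needs no additional assumption, so correlated measurements on the same people are no obstacle. Bonferroni's usual advantage, simple simultaneous confidence intervals, does not apply because the SAP plans none for these tests.

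The contrast most likely to benefit is baseline to 1 month. In the earlier pneumonia program, trust in pharmacists as immunizers rose from 16% to nearly 50% immediately afterwards (protocol section 2.2.3), and section 2.7.2 says the trust gains did not outlast the post-test. If that pattern recurs, the other two pairs may be rejected easily while baseline to 1 month is borderline. At stake is the chance of missing a real but modest 1-month improvement within an arm.

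**Working it through.** **Inputs from the documents.** Three pairs per item and arm; alpha 0.05; 158 enrolled per arm ("thus scaling up by 30% yields a total sample size of 316 (158 in each arm"), planned to leave 121 evaluable ("This difference is detectable at a power of 0.8 with 121 participants in each arm of the study"); attrition about 30% (section 2.7.3); a missing 1-month value replaced by the post-test value (SAP Table 1). Section 2.2.3 supplies the 16% and roughly 50% for trust, and a 21% baseline for one belief that more than doubled. **Assumed:** two-sided tests (the SAP does not say; the protocol plans two-tailed tests), the 1-month shares, the remaining post-test shares, and within-person correlation of 0.3 to 0.5.

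**1. The plan's figure.** 0.05/3 = 0.01667, which reproduces 0.0167.

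**2. Upper limit on the gain.** Under a normal approximation, with standardized effect θ, power at level a is Φ(θ − z(a)). Two-sided critical values are z(0.0167) = 2.394, z(0.025) = 2.241 and z(0.05) = 1.960. Maximizing the power difference over θ:

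- If one other pair is rejected (0.025 against 0.0167): at most 6.1 points.
- If both other pairs are rejected (0.05 against 0.0167): at most 17.2 points, from 41.4% to 58.6%.

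For example, a contrast with 80% power at 0.05 has 71% at 0.025 and 66% at 0.0167. Baseline to 1 month gets the full 0.05 only if both other pairs, including post-test to 1 month, are rejected. If the improvement is truly maintained, that last pair is null, so baseline to 1 month usually reaches 0.025 at best.

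**3. Simulated baseline-to-1-month power.** Paired yes/no item, 158 per arm, normal test on discordant pairs; ranges run over correlations 0.3 to 0.5. Shares are baseline/post-test/1 month. Carry-forward replaces 30% of 1-month values at random.

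| Shares (%) | Post-test gain lost | Bonferroni, complete | Holm, complete | Gain, complete | Gain, carry-forward |
|---|---|---|---|---|---|
| 21/33/33 | 0 | 59–69% | 62–72% | about 3 | about 3 |
| 16/30/25 | 5/14 = 36% | 41–48% | 47–54% | 6–7 | 5–6 |
| 21/45/33 | 12/24 = 50% | 58–69% | 72–81% | 12–13 | 5–7 |
| 21/45/31 | 14/24 = 58% | 43–52% | 57–67% | 14–15 | 8–10 |
| 16/50/25 | 25/34 = 74% | 41–49% | 58–66% | 16–17 | 3–5 |

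In the last three rows carry-forward raises Bonferroni power itself, to 83–90%, about 75–84% and 91–96% respectively, so less is left to gain. At 111 per arm (158 × 0.7, completers only, which is not the SAP's analysis), the faded rows gain about 10 to 17 points. One cell reached about 19 because a yes/no item is discrete.

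**4. Check with signed-rank tests** on five-level and yes/no items, 121 and 158 per arm, correlation 0.5, complete data:

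- Fully maintained: 1 to 4 points.
- Mild fade: 4 to 7.
- Half faded: 8 to 13.
- Two-thirds or more faded: 12 to 17.

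With carry-forward the half-faded cases gave 5 to 9 points. The more heavily faded cases gave roughly 1 to 14 over all settings tried, the larger values coming from yes/no items.

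**5. Error control.** With no true baseline-to-1-month change (21/45/21) and complete data, Holm rejected that contrast in about 5% of runs. With 30% carry-forward and the same null, rejection rose to 15–25% under Bonferroni and 26–41% under Holm (111 to 158 per arm). Post-test values are standing in for 1-month values; the inflation comes from carry-forward, and Holm's looser threshold passes more of it through.

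**The case against.** The strongest reply is that Bonferroni is valid and explicitly specified, and that this is a preference about a secondary analysis. That stands: nothing in the plan is wrong on this point. The SAP is dated March 2020 and written in the past tense, so adopting a looser threshold after seeing results would be post hoc. That also stands and shapes the fix.

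Three stronger readings are tempting, and the documents do not support them.

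- **That the plan loses 10 to 19 points of power for sustained change.** Gains of 10 or more require a large post-test rise followed by a marked fade, with complete data. For a fully maintained improvement the gain is about 1 to 4 points. Nineteen exceeds the normal-approximation ceiling of 17.2 and appeared only in one small-sample cell. Nor can the 16% to nearly 50% rise be carried over to every item or to PEER: it concerns trust in pharmacists after a pharmacist-led program.
- **That Holm would help answer whether trust is sustained.** Section 2.7.2 of the protocol frames this as PEER versus PHARM. The SAP compares beliefs between arms with Chi-square or Fisher's exact tests, which this change leaves alone.
- **That the within-arm knowledge tests are uncorrected.** The SAP states no threshold there, but its general Bonferroni rule may cover them. In simulation, three uncorrected tests gave about a 12% family-wise error rate, but that assumes no knowledge change at any time, whereas the earlier program reported a 54% increase. What remains is an ambiguity to settle in wording.

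**Conclusion.** The point holds as an optional efficiency gain. Holm rejects everything that the fixed 0.0167 rejects, sometimes more, at the same 5% family-wise error within each three-pair family. For baseline to 1 month the gain is about 1 to 7 points if the post-test improvement largely lasts, and about 10 to 17 if a large improvement mostly fades and 1-month data are complete. Under the SAP's carry-forward at 30% missing and 158 per arm, the three faded share scenarios gain about 4 to 10 points (3 in the lowest single run).

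These sizes depend on assumed 1-month shares and correlations; that Holm is never worse does not. Either procedure protects three pairs for one item in one arm, not all items and both arms. Because carry-forward inflates this contrast, any additional Holm rejection at 1 month needs reading with that in mind.

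**What to change.** In the Beliefs section of the SAP, replace the fixed 0.0167 with:

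> For each item and arm, the three pairwise p-values are ordered and tested by Holm's procedure (0.0167, then 0.025, then 0.05, stopping at the first non-rejection).

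State the same rule in the Knowledge section for the three within-arm comparisons on each score, which also removes the ambiguity about their threshold. If results have already been seen, keep Bonferroni as the specified analysis and report Holm beside it as a labelled sensitivity analysis.

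The cost is a sentence in each section and no new data. Holm has no simple matching simultaneous confidence intervals, but none are planned for these tests. The carry-forward rule needs separate attention; this change does not address it.

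### No between-arm comparison of beliefs or trust in the SAP measures change from baseline or adjusts for baseline, although the protocol frames its sustained-trust question as change (secondary outcome, minor)

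*SAP*

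**What the plan says.** **Protocol.** Objective 2 (section 2.1) compares the two arms on how well they improve beliefs. Section 2.7.2 counts trust in information sources among the belief measures. It says "the change in beliefs from baseline to post test and one month after the intervention will be assessed" in both arms, "to determine whether the PEER group experiences a greater level of sustained trust vs. the PHARM group".

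**SAP, Overview.** "Secondary measures included between-group examinations of beliefs, trust, and activation at all 3 time points (BL vs. PT and M1" (the SAP's bracket closes there). The unit of allocation is the session date: "randomization to PHARM or PEER performed at the program date level".

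**SAP, Beliefs.** There are three elements:
- The percentage answering Completely Agree "to each item at each timepoint was calculated and compared between PHARM and PEER, as in our PPPP study".
- Signed-rank tests "comparing within-group changes in beliefs across timepoints applying Bonferroni correction", at 0.05/3 = 0.0167.
- Chi-square or Fisher's exact "tests were used to compare beliefs between groups at each timepoint, depending on expected cell counts". This sentence names no cut-point, so I read it with the first element as a test of the Completely Agree percentage.

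Trust has no analysis section of its own.

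**SAP, Knowledge.** The arms are compared by rank-sum test at each timepoint and also, separately, on differences across timepoints.

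**The concern.** The protocol's question is between arms and is framed as change from baseline. The SAP measures change only within arms and compares arms only on levels. Setting one arm's signed-rank p-value beside the other's does not compare the arms.

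The knowledge paragraph shows that the SAP treats a per-timepoint comparison and an across-timepoint comparison as different analyses. Beliefs receive only the first.

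The one-month contrast matters most. Section 2.7.2 reports that trust gains in the prior PPPP study did not last beyond the post-test, so whether trust is sustained is decided at one month. With possibly only a few randomised dates, the arms may start at visibly different levels of trust. Baseline responses are collected, but no planned follow-up contrast uses them as a covariate.

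**Working it through.** **1. The plan's own figure.** 0.05/3 = 0.0167 reproduces. It is attached only to the within-group belief tests.

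**2. Question against method.**
- Change within each arm: asked (section 2.7.2) and tested (signed-rank).
- Level between arms at baseline, post-test (PT) and one month (M1): tested (chi-square/Fisher).
- Change between arms, or follow-up adjusted for baseline: asked in the purpose clause of section 2.7.2, with no test given. For knowledge a test across timepoints is given.

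**3. Inputs.** From the documents: 158 planned and 121 evaluable per arm (section 2.7.3); 16% baseline trust in pharmacists as immunizers and 21% baseline belief in vaccine efficacy (PPPP, section 2.2.3); three or six PHARM groups (section 2.5). Ten peer educators with 5–6 participants each reach 50–60 people per round, so 158 PEER participants need about three rounds. Assumptions: one date per group or round, ICC 0.02, item correlation r between baseline and follow-up of about 0.2–0.4, and the M1 percentages.

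**4. Chance baseline difference.** With three dates per arm of 158/3 = 52.7 people, SD = √[0.16 × 0.84 × 2 × (ICC + (1 − ICC)/52.7)/3].
- ICC 0: 4.1 points.
- ICC 0.02: 5.9 points.

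The share carried into M1 is the slope r × SD(M1)/SD(baseline). This runs from 0.2 × 1 = 0.20 (M1 at 16%) to 0.4 × 0.500/0.367 = 0.55 (M1 at 50%). The carry-over is then 0.8–2.3 points without clustering and 1.2–3.2 points with it.

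**5. Level and change can differ.** Suppose PHARM goes from 21% to 45% and PEER from 30% to 45%, with 158 per arm. The follow-up level test gives p = 1.00, while the changes differ by 9 points (p = 0.15 at r = 0.3, no clustering). A 9-point baseline gap is at the edge of the 95% chance range: 1.96 × √(2 × 0.21 × 0.79/158) = 9.0 points.

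**6. Precision, relative to comparing follow-up levels alone.**
- Baseline-adjusted variance, 1 − r²: 0.96 at r = 0.2 and 0.84 at r = 0.4.
- Raw-change variance, 2(1 − r): 1.6 and 1.2.

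At these correlations adjustment helps and raw change scores hurt.

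**7. Power without clustering.** Simulation of 6,000 runs per row, 121 per arm, 16% at baseline, two-sided 0.05; planned chi-square, then logistic regression adjusted for baseline Completely Agree:

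| M1 percentages | item r about 0.2 | item r about 0.4 |
|---|---|---|
| 16 vs 28 | 0.624 → 0.638 | 0.619 → 0.708 |
| 30 vs 45 | 0.685 → 0.700 | 0.687 → 0.759 |
| 42 vs 57 | 0.628 → 0.655 | 0.630 → 0.702 |

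The gains are 0.01–0.03 and 0.07–0.09.

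**8. Power at date level.** Noncentral t, 158 per arm, ICC 0.02, illustrative effect 0.4 SD (20/50, the knowledge assumption in section 2.7.3, not a belief effect). SE² = Σ over arms of (ICC + (1 − ICC)/m)/k, with k dates of m people; adjustment multiplies SE by √(1 − r²). The lower adjusted value loses one degree of freedom.

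| Dates | unadjusted | r = 0.2 | r = 0.4 |
|---|---|---|---|
| 3 vs 3 (SE 0.160, 4 df) | 0.475 | 0.42–0.49 | 0.46–0.54 |
| 6 vs 3 (SE 0.150, 7 df) | 0.632 | 0.63–0.65 | 0.68–0.71 |

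**9. Type I error.** Without clustering both tests in step 7 hold about 0.05. With ICC 0.02 the design effect is 1 + 51.7 × 0.02 = 2.03. A nominal 5% test that ignores date then has a true level of about 2[1 − Φ(1.96/√2.03)] = 0.17.

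**The case against.** The case for leaving the plan as it is has four parts.

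**Baseline is compared.** The three timepoints include baseline, so the arms are tested there and an imbalance would be seen. This stands: a reader might infer that the SAP never compares baseline beliefs between arms, and that is wrong. Seeing an imbalance does not, however, bring it into the follow-up contrast.

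**The overview can be read as consistent.** For knowledge it speaks of change. For beliefs, trust and activation it speaks of examinations at all three timepoints, and activation is also tested per timepoint. A reader might infer an outright contradiction inside the SAP, but the bracketed reference to baseline is ambiguous and does not establish one. The gap rests on section 2.7.2 of the protocol, Objective 2 and the contrast with knowledge. Even in section 2.7.2, the words on assessing change in both arms are met by the signed-rank tests; only the purpose clause is not.

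**Randomisation makes the M1 level comparison valid.** As an estimate, yes. A reader might infer that it is biased or cannot answer the trust question. Neither follows: the example in step 5 shows the effect of a chance imbalance, not bias. Hypothesis 2 (section 2.1.1) is about improvement in each arm and is served as planned.

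**The gain is small.** This also stands. Variance reductions of a quarter or a half need correlations of 0.5–0.7, above the 0.2–0.4 assumed here for single binary items. With few dates, ignoring program date in the test is the larger problem, and baseline adjustment alone does not cure it.

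**Conclusion.** The point holds as a minor one. The protocol poses a between-arm question about change in beliefs and trust, and the SAP supplies no between-arm analysis of change or adjusted for baseline. That part is textual and needs no assumption.

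Its consequence is limited. The M1 level comparison remains a valid estimate in principle, but it carries an uncorrected chance baseline difference (SD about 4–6 points, of which roughly 1–3 points would pass into M1) and is usually somewhat less precise. The power gain from adjusting is 0.01–0.09 under individual randomisation. It is roughly nil, possibly slightly negative, with three dates per arm. These sizes rest on assumed correlations, ICC, M1 percentages and number of dates, none of which the documents give. The primary knowledge result is unaffected.

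**What to change.** Add to the SAP's Beliefs section:

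- For each belief and trust item, a between-arm comparison at PT and at M1 adjusted for that item's baseline response. Logistic regression on Completely Agree would serve, reporting the adjusted percentage-point difference with its interval.
- Inference that respects program date and suits few clusters: a date-level analysis of baseline-adjusted residuals, or a permutation test over dates. With 3 vs 3 dates there are only 20 allocations, so a two-sided permutation p-value cannot fall below 2/20 = 0.10; there the date-level analysis is the more usable.
- The M1 trust contrast named as the protocol's sustained-trust comparison, with the other item-level contrasts labelled exploratory.
- A rule for a missing item-level baseline, since the ITT sample requires only one or more "documented response from the baseline survey".
- A sensitivity analysis on observed M1 responses, because the SAP's Table 1 carries PT or baseline values into M1 and a carried value says nothing about sustained trust.

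Keep the planned chi-square/Fisher percentages for comparability with PPPP.

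**Cost.** No new data, only SAP text and programming. Models for sparse items may be unstable, and more item-level tests add multiplicity: an assumed 10 items at two timepoints gives 20 tests, with 20 × 0.05 = 1 false positive expected at 0.05 if no item differs. The SAP is written in the past tense; if the data have been seen, the analysis should be labelled supplementary.

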2.1 Objectives

- Compare the efficacy of PHARM vs. PEER at improving participant's knowledge regarding vaccine-preventable diseases
- Compare the efficacy of PHARM vs. PEER at improving participants' beliefs about vaccination
- 3) Measure the costs of PHARM and PEER from the senior center perspective
- 4) Compare the percent of participants taking activation step(s) to get vaccinated following receipt of PHARM vs. PEER
- 5) Determine the extent to which participants are satisfied with and trust the PHARM vs. PEER interventions

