2.1.1 Hypotheses

- PHARM and PEER will achieve similar improvements in older adults' knowledge of vaccine preventable diseases (primary hypothesis)
- PHARM and PEER will improved beliefs about vaccinepreventable disease
- 3) **PEER will be a lower cost approach** to educating participants in the senior center compared to PHARM
- 4) PHARM and PEER will result in similar rates of participants taking one or more activation step(s) to obtain vaccination
- 5) Participants will be highly satisfied with the PHARM and PEER interventions

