Intervention costs for PHARM and PEER will be calculated as the monetary value of time and materials required to train involved personnel, and deliver PHARM and PEER as well as personnel travel costs. Data on personnel time requirements for delivering PHARM and PEER will be collected in real time by

trained staff members using time logs which document the time and staff members required for training and delivery of the program. These data will be monetized using the hourly wage rates plus fringe benefit costs of the involved personnel. Other costs include materials such as signage, a modest participant giveaway such as medication reminder cards and pill box, printing/duplication, and food/refreshments. All costs will be reported in \$US 2017, consistent with the intervention time period.

Activation (Objective 4):

Participant activation will be measured as percent of participants who report taking one or more actions towards receiving vaccination at one month post-intervention, such as discussion with a healthcare provider (physician/pharmacist) or friends/family and/or receiving vaccination for either pneumonia or zoster. For participants who report vaccination, we will report which (pneumonia, zoster, or both). Influenza vaccination activation will be excluded from this measure since influenza vaccination is widely promoted through other initiatives which could influence activation, such as onsite flu shots at CIP.

Satisfaction (Objective 5):

Satisfaction measures will include **participants' overall satisfaction** with the content and delivery of PEER vs PHARM, the extent to which the participant felt **engaged**, and their **satisfaction with information received**. Satisfaction will be measured only at post-test using a simple 5-10 item satisfaction survey adapted from our prior research.

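### The SAP specifies no analysis of the protocol's one-month activation measure (Objective 4), and its carry-forward rule fills missing one-month answers with answers given on the program day

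*SAP*

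**What the plan says.** **Protocol.** Objective 4 (2.1) is to "Compare the percent of participants taking activation step(s) to get vaccinated following receipt of PHARM vs. PEER". Hypothesis 4 (2.1.1) expects that "PHARM and PEER will result in similar rates of participants taking one or more activation step(s) to obtain vaccination". The definition is in 2.7.2: "Participant activation will be measured as percent of participants who report taking one or more actions towards receiving vaccination at one month post-intervention". The actions named there are talking to a healthcare provider or to friends and family, and being vaccinated against pneumonia or zoster. It adds that "Influenza vaccination activation will be excluded from this measure", because other initiatives also promote flu shots. For people who report vaccination, the protocol will also say which of the two vaccines they had. The same section puts baseline (BL) and post-test (PT) on the day of the program and the one-month survey (M1) by telephone.

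**SAP.** The Overview lists activation among the secondary measures, at all three timepoints. The Activation section describes Chi-Square or Fisher tests "at each timepoint to assess between-group differences in proportions of participants planning actions, including planning vaccination and planning to speak with a doctor". The sentence goes on to actions taken: vaccinations obtained and conversations held. A further analysis takes participants with no positive vaccination report at PT. It compares vaccination at PT and M1 for each vaccine type, and each discussion item at each timepoint.

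For missing PT or M1 data, the Overview says that "the matrix below was used to carry forward observations". When PT is present and M1 is missing, the Table 1 entry is "Absent Utilize PT Data". When both are missing, baseline is used for both. No outcome is exempted.

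**The concern.** There are two linked problems.

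1. **Endpoint.** The protocol commits to one binary outcome at one time. The SAP replaces it with a set of item-level and per-vaccine comparisons at several times, mixing intentions with actions, and does not say how they combine or which one leads. A reader could not tell which result answers Objective 4, and the choice could be made after the results are seen.
2. **Missing data.** Activation is an event that can only happen after the program. An answer given on the program day, before or just after the session, says nothing about the following month. Carrying it into M1 enters a value that cannot be a measurement of the outcome.

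Activation is a secondary measure, so the primary knowledge result is not affected. What is at stake is whether Objective 4 gets the analysis that the protocol defined, and whether the M1 activation figures mean what their label says.

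**Working it through.** **Step 1. Definition against analysis.**

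| Feature | Protocol 2.7.2 | SAP, Activation |
|---|---|---|
| Actions or plans | actions taken | planned actions and actions taken |
| Combination | at least one action | no rule stated |
| Timepoint | one month | each timepoint (M1 included), no lead |
| Influenza vaccination | excluded | no exclusion stated; vaccine types tested separately in the subset |

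The components are present, so the composite can be built from the data. But the item results do not determine it. Take four assumed item rates of 20%, 30%, 15% and 35%. The share with at least one can lie anywhere from the largest, 35%, to the sum, 20 + 30 + 15 + 35 = 100%. If the items were independent it would be 1 − 0.80 × 0.70 × 0.85 × 0.65 = 0.69.

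**Step 2. What a carried answer can record.** BL and PT are both same-day, so neither can contain an action taken in the following month. In the SAP's subset, membership requires no positive vaccination report at PT. A PT answer carried into M1 there can never be a positive report.

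**Step 3. How many answers could be carried.** The documents give no M1 dropout for this trial. The planning figures in Protocol 2.7.3 are:
- Loss in the prior project: (203 − 143)/203 = 60/203 = 29.6%, which reproduces the stated figure. Follow-up there ran to 3 months (2.2.3), so loss at one month may be lower.
- Enlarging 121 to 158 per arm allows for losing 37/158 = 23.4%.

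Over an assumed range of 15% to 30%, 158 × 0.15 = 23.7 to 158 × 0.30 = 47.4, or about 24 to 47 carried answers per arm.

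**Step 4. Effect on the difference (illustration).** Let m be the share missing at M1, equal in both arms. Let D_c and D_d be the true differences between arms among completers and dropouts, and q1 and q2 the positive shares of the carried answers.

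- True difference = (1 − m) × D_c + m × D_d
- Reported difference = (1 − m) × D_c + m × (q1 − q2)

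Carried answers count as no (q1 = q2 = 0) and dropouts resemble completers (D_c = D_d = 10 points):
- m = 0.15: 0.85 × 10 = 8.5
- m = 0.234: 0.766 × 10 = 7.7
- m = 0.30: 0.70 × 10 = 7.0

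Unequal dropout, same true rate p in both arms, carried answers count as no: false gap = p × (m2 − m1). With an assumed p of 40% and dropout of 25% and 35%, this is 0.40 × 0.10 = 4.0 points.

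Other assumptions, with m = 0.30, D_c = 10 and carried answers as no:
- D_d = 0: true 7.0, reported 7.0 (no bias).
- D_d = −10: true 0.7 × 10 − 0.3 × 10 = 4.0, reported 7.0 (overstated).

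Composite in all participants, where carried answers may be positive, with m = 0.30 and D_c = D_d = 10: q1 − q2 of −10, 0, +10 or +20 points gives a reported 4.0, 7.0, 10.0 or 13.0.

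**The case against.** The SAP does more than its planned-action wording suggests. It tests actions taken, and M1 is one of its timepoints. Testing each vaccine type separates pneumonia and zoster from influenza in the subset and partly meets the protocol's wish to report which vaccine was received. All of this stands. A reader might infer that the SAP swaps actions for intentions, or that it counts influenza vaccination in the Objective 4 result. The documents support neither: what is absent is the combining rule, the lead timepoint and a stated exclusion.

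On missing data, a reader might infer that carry-forward always pushes the arms together and so favours the similarity hypothesis. The documents do not support that either. The questionnaire wording and the scoring of unknown vaccination status are not shown, and the cases above include no bias, overstatement and understatement. For all participants the direction is open.

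The illustrated distortions are also modest against sampling error. With 158 per arm and an assumed rate of 40% in both, the simple standard error is √(2 × 0.40 × 0.60/158) = 0.055, or 5.5 points. That exceeds both the shrinkage of 1.5 to 3.0 points and the 4.0-point false gap. This too is fair, but it does not rescue the rule: a systematic error is not covered by the confidence interval, and the point that a same-day answer cannot measure a later action needs no assumption about rates.

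**Conclusion.** Both parts hold on the text. The SAP states no analysis that answers Objective 4 as Protocol 2.7.2 defines it, and Table 1, applied as written, places same-day answers in the one-month activation data. In the subset not reporting vaccination at PT, a carried PT answer can never be positive.

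The size can only be illustrated. If carried answers are scored as no, dropouts resemble completers and dropout is equal at 15% to 30%, a true 10-point difference is reported as 8.5 to 7.0 points, towards the similarity hypothesis. Unequal dropout creates a gap that is not there. Outside those assumptions, and for the composite in all participants, the sign of the bias is not determined. The change should be made, though it concerns a secondary objective.

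**What to change.** - **Objective 4 analysis.** Specify the protocol's composite at M1 (at least one action taken for pneumonia or zoster, influenza vaccination excluded) in all participants by randomised arm, with a risk difference and confidence interval.
- **Missing M1 answers.** For actions taken and vaccination, do not carry PT or BL answers into M1. Use observed M1 data or multiple imputation, and report M1 missingness by arm.
- **Sensitivity analysis.** Count missing as no. In the subset, for people with PT data, this matches the present fill if a non-positive answer is scored as no; the change there is which analysis leads. State how unknown vaccination status is scored.
- **Other results.** Present planned actions, single items and per-vaccine comparisons as supportive.

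The cost is SAP wording and re-analysis of data already collected. The observed-data analysis uses fewer people: at 30% loss, 158 × 0.70 is about 111 per arm. It and the imputation rely on missingness being explained by observed data, which the sensitivity analysis only partly probes.
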